7.6.8 Response duration

This will be measured from the time of randomization, or until the first date that recurrent or progressive disease is objectively documented. Patients who have not had PD/iCPD at the time of final analysis will be censored at the date last known to be alive and progression-free.

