ORR is defined as the percentage of patients with a confirmed CR or PR. The proportion of participants achieving at least PR will be summarized with corresponding 95% CI for each treatment arm. The difference between the trial arms in the proportion of participants achieving at least PR will also be presented with corresponding 95% CI. The difference between participants achieving at least PR and remaining participants will be assessed using logistic regression adjusting for treatment group and stratification factors. Odds ratios with corresponding 95% CI and *p*-values will be presented for all variables incorporated in the model.

SSCRR is defined as the percentage of patients with a confirmed resection of metastatic disease with microscopically free margin (R0). Corresponding analyses as those to be performed for ORR will be applied for SSCRR.

DOR is defined as the time from the first documentation of CR/iCR or PR/iPR to disease progression. DOR Kaplan-Meier curves will be drawn and compared by log-rank test. The median DOR with corresponding 95% CI will be presented by treatment group. Stratified analyses will be performed as well. The Cox proportional hazards model, adjusting for the stratification factors, will also be used to compare DOR between the treatment groups. HR, 95%CI and *p*-values will be presented for all variables incorporated in the model.

OS is defined as the time from randomization to death of any cause. The same analyses as for DOR will be performed for OS.

The assumptions for the statistical method considered will be assessed by using standard techniques. In the case the assumptions are not met, the necessary adjustments for methods specified above will be introduced and reported.

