### 5. Analysis

#### 5.1. End point definitions

*Primary end point:* PFS; radiologic assessment every 8 weeks, according to the Response Evaluation Criteria in Solid Tumors (RECIST) and the RECIST consensus guideline for assessment of response to immune-modulating therapies, iRECIST.

*Secondary end points:*

Safety: incidence of adverse events (AE), as reported according to Common Terminology Criteria for Adverse Events (CTCAE) version 4.0 recorded on ongoing basis.

Tolerability: AE grading, as assessed by CTCAE v4.0 recorded on ongoing basis.

ORR: the percentage of patients with a confirmed complete response (CR) or partial response (PR).

DOR: the time from the first documentation of a CR or PR to disease progression.

SSCRR: the percentage of patients with a confirmed resection of metastatic disease with microscopically free margin (R0).

OS: the time from randomization to death of any cause.

QoL: assessment undertaken at study enrolment, completion of the active therapy of the first treatment sequence (after 16 weeks), and disease progression, using the consensus modules EORTC QLQ-C30, EORTC QLQ-CIPN20, and EQ-5D-5L.

*Tertiary end point:* Cost estimate; evaluation of the healthcare costs (relating to the sequencing procedures and administered medication) and health effects (quality-adjusted life years), expressed as incremental cost-effectiveness ratio, of the sequential therapy relative to the control group as comparator.

*Exploratory end points:* Various analyses will be undertaken for exploratory end points listed in 1.2.

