#### 5.2. Analysis methods

*Main statistical analyses.* The main statistical analysis is planned after the last patient has fulfilled the pre-defined follow-up period. PFS will be calculated from the day of randomization to first recorded disease progression according to RECIST v1.1 or when applicable iRECIST, or death. Patients who have not had disease progression at the time of final analysis will be censored at the date last known to be alive and progression-free. The analyses will compare the treatment groups in total as well as groups stratified by primary tumor sidedness and (K)RAS/BRAF mutation status.

*Interim analyses.* Interim analyses will apply to data on safety, tolerability, possible detrimental effects, and curative outcomes, and will be based on purely clinical judgment by the External Data and Safety Monitoring Committee. These types of data will be reported as the number of events.

*Descriptive statistics.* Demographic and clinical characteristics will be presented as means and standard deviations, medians with minimum and maximum values, or frequencies and percentages, as appropriate. Further statistical analyses will be separated to primary analyses, including only comparison of primary end point between two treatment arms, and secondary analyses, including stratified analyses on primary and secondary end points as well as number of analyses on secondary end points.

*Primary analysis.* Median PFS time will be compared between study arms by drawing Kaplan-Meier survival curves and performing log-rank test. HR with the corresponding 95% CI and p-values will be estimated by Cox proportional hazards model.

*Secondary analyses.* Distribution of PFS times stratified by the primary tumor sidedness and (K)RAS/BRAF mutation status will be illustrated graphically by Kaplan-Meier curves and compared by log-rank test. To assess the hazard rates for disease progression within each strata, Cox proportional hazards model will be estimated and, if appropriate, adjusted for relevant covariates. The results will be presented as HR with the corresponding 95% CI and p-values.

Safety. The number of serious adverse events (SAE) will be summarized and presented by trial arm. In addition, information will be given on the number of SAE per participant, together with details on the causality, expectedness, and outcome of each SAE experienced. Summaries of suspected unexpected serious adverse reaction (SUSAR) events will also be presented by trial arm.

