Tolerability. Summaries by trial arm will be produced to show the proportion of participants experiencing each grade of CTCAE toxicities overall and during each treatment cycle. For more detailed summaries, this information will also be broken down into the different types of toxicities.

QoL. This will be summarized for each treatment arm at study enrolment, completion of the active therapy of the first treatment sequence (after 16 weeks), and disease progression, using the consensus modules EORTC QLQ-C30, EORTC QLQ-CIPN20, and EQ-5D-5L. The data will be illustrated graphically and presented as mean scores with 95% CI at separate time points. The differences in QoL between two treatment arms throughout the study period will be assessed by estimating a linear mixed model with fixed effects for time and treatment arm and the interaction between these two. Random effects for patients will be included. A significant interaction will quantify differences between the groups and serve as an omnibus test.

Safety and tolerability in the treatment arms will be compared by  $\chi^2$  or Fisher's exact test, as appropriate.

ORR is defined as the percentage of patients with a confirmed CR or PR. The proportion of participants achieving at least PR will be summarized with corresponding 95% CI for each treatment arm. The difference between the trial arms in the proportion of participants achieving at least PR will also be presented with corresponding 95% CI. The difference between participants achieving at least PR and remaining participants will be assessed using logistic regression adjusting for treatment group and stratification factors. Odds ratios with corresponding 95% CI and p-values will be presented for all variables incorporated in the model.

SSCRR is defined as the percentage of patients with a confirmed resection of metastatic disease with microscopically free margin (R0). Corresponding analyses as those to be performed for ORR will be applied for SSCRR.

DOR is defined as the time from the first documentation of CR/iCR or PR/iPR to disease progression. DOR Kaplan-Meier curves will be drawn and compared by log-rank test. The median DOR with corresponding 95% CI will be presented by treatment group. Stratified analyses will be performed as well. The Cox proportional hazards model, adjusting for the stratification factors, will also be used to compare DOR

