between the treatment groups. HR, 95%CI and p-values will be presented for all variables incorporated in the model.

OS is defined as the time from randomization to death of any cause. The same analyses as for DOR will be performed for OS.

The assumptions for the statistical method considered will be assessed by using standard techniques. In the case the assumptions are not met, the necessary adjustments for methods specified above will be introduced and reported.

*Analysis of other end points.* Cost modeling and validation will apply a model specifically developed for CRC by Investigator at Health Services Research Center, Akershus University Hospital [Joranger et al., 2015].

For *exploratory analyses*, appropriate statistical methods will be applied to analyze the various outcome measures.

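### Duration of response leaves out death, so a responder's death without documented progression is censored, and its between-arm test covers responders only

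*SAP*

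**What the plan says.** The end point is defined in four places: the objectives table in Protocol section 2, Protocol 10.4.5, SAP 5.1 and SAP 5.2. SAP 5.1 has "DOR: the time from the first documentation of a CR or PR to disease progression". Protocol 10.4.5 has "DOR is defined as the time from the first documentation of CR/iCR or PR/iPR to disease progression", and SAP 5.2 repeats that sentence. None of the four names death.

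PFS is handled differently. SAP 5.2 runs it to "first recorded disease progression according to RECIST v1.1 or when applicable iRECIST, or death".

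The SAP gives no censoring rule for DOR. The only rule for response duration is in Protocol 7.6.8. It censors anyone without PD or iCPD when the final analysis is done, using the latest date on which that patient was known to be living without progression. The same section gives another start for the clock: "This will be measured from the time of randomization, or until the first date that recurrent or progressive disease is objectively documented".

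For the comparison, SAP 5.2 plans a log-rank test: "DOR Kaplan-Meier curves will be drawn and compared by log-rank test". It then adds a model with treatment arm as a term: "The Cox proportional hazards model, adjusting for the stratification factors, will also be used to compare DOR". On the output of that model it says: "HR, 95%CI and p-values will be presented for all variables incorporated in the model". SAP 2.4 places comparisons between arms in a superiority framework, SAP 3.1 makes no multiplicity adjustment, and SAP 5.4 plans no further analyses. Nothing describes the DOR comparison as descriptive.

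**The concern.** There are two separate problems.

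First, a patient who responds and then dies without documented progression has had no DOR event under the written definition. Under the Protocol 7.6.8 rule that patient is censored, and the Kaplan-Meier method then treats the patient as someone who could still progress later. A death in response, including one from toxicity, would count as no failure, and median DOR would look longer than the time patients actually spent alive and in response.

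Second, only patients with a response have a start date, so the log-rank test and Cox model compare responders in one arm with responders in the other. Response occurs after randomisation. If the arms have different response rates, or select different kinds of patient into response, the two groups can differ in prognosis even when treatment does not affect duration. Adjusting for sidedness and (K)RAS/BRAF status does not restore what randomisation gave.

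At stake are a median that is too long and a hazard ratio and p-value that cannot be read as a treatment effect.

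**Working it through.** **The plan's own figures.** The documents state no number for DOR. The only design calculation is for PFS, and it reproduces. Freedman's formula with HR 0.5, two-sided 5% and 80% power gives ((1+0.5)/(1-0.5))² × (1.960+0.842)² = 9 × 7.85 = 70.6, so 71 events. Then 71/0.90 = 78.9, so 79 patients or 40 per arm, and 80 × 1.05 × 1.20 = 100.8, close to the stated 100. The point below does not rest on this.

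**Step 1: effect of censoring deaths.** Let responders progress at a constant hazard p and die without progression at a constant hazard d. The share of first events that are deaths is f = d/(p+d).

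- Median time to progression or death: ln 2/(p+d).
- Kaplan-Meier median when deaths are censored: ln 2/p = ln 2/[(p+d)(1-f)].
- Ratio: 1/(1-f).

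The documents do not give f, so a range is assumed. The true median of 9 months is for illustration only.

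| f (assumed) | 1/(1-f) | Reported median if the true one is 9 months |
|---|---|---|
| 0% | 1.00 | 9.0 |
| 5% | 1.05 | 9.5 |
| 10% | 1.11 | 10.0 |
| 20% | 1.25 | 11.25 |

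If f is the same in both arms, the factor cancels in the hazard ratio. If it differs and the total hazards are equal, the progression-only hazard ratio is the ratio of the (1-f) terms. With an assumed 20% in one arm and 5% in the other, it is 0.80/0.95 = 0.84 with no true difference.

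**Step 2: effect of comparing responders only.** The documents give no response rates, so these are also assumed. In the simulation, the log hazard after response varies between patients with standard deviation 0.5 or 1.0 around a median of 9 months. It follows the same law in both arms, and response has a correlation of 0.6 with prognosis. Treatment has no effect on duration.

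- Medians at response rates 60% v 40%: 10.7 v 11.7 months (SD 0.5) and 12.2 v 14.8 months (SD 1.0). The arm with fewer responders looks better by 1.0 to 2.6 months.
- Log-rank rejection rate at 50 per arm, 4,000 runs, follow-up uniform over 12 to 28 months: 4.8% to 5.5% with equal response rates (50% v 50%), and 5.3% to 7.4% with unequal rates (60% v 40%, 50% v 30%, 50% v 70%, and similar). The Monte Carlo standard error is √(0.05 × 0.95/4,000) = 0.3 percentage points.

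A second model, with identical PFS in both arms, response rates 50% v 35% and 48 patients per arm, gave rejection rates of about 6% at correlation 0.3 and 8% at 0.6, against about 6% at zero. It times patients from randomisation, so it serves only as a cross-check on the rejection rate.

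**Step 3: information in the comparison.** With 95 analysed patients, an assumed response rate of 30% to 60%, and 70% to 90% of responders with an event, there are 20 to 51 events (95 × 0.30 × 0.70 = 20; 95 × 0.60 × 0.90 = 51). Schoenfeld's formula gives power of 34% to 70% for HR 0.5.

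**The case against.** The SAP does not say that deaths are censored. That follows only when its definition is read with Protocol 7.6.8, and the censoring sentence there is nearly the same as the one used for PFS, where death is plainly an event. One could argue that the authors meant the same for DOR. This stands as a comment on intent. It does not settle the text, because PFS names death as an event before the censoring rule applies, and no DOR definition does. A programmer following the documents would censor the death.

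The share f may be small. Protocol 7.6.5 has imaging every 8 weeks in both arms, including treatment breaks and after discontinuation in patients who have not progressed, with earlier scans allowed on suspected progression. Progression that precedes death will often be documented. This stands: a reader might infer from the table that the plan overstates durability by 25%, but that needs one in five responder events to be death without progression, and nothing in the documents supports that figure.

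A reader might also infer that the responder-only test is likely to give a false positive. The simulations do not support that at plausible correlations. Rejection rose to 17% to 19% only at a correlation of 1.0, where responders are exactly the patients with the longest PFS.

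Nor do the documents make durable response the central hypothesis. The hypothesis in Protocol section 2 is an improved outcome over standard of care, and the primary end point is PFS. Durable effects are raised in the risk/benefit text (Protocol 4.6). DOR is one of several secondary end points. PFS and OS both count death from randomisation, and response rates are reported by arm, so an imbalance in responders would be visible.

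**Conclusion.** The point holds in two parts of modest weight. As written, DOR omits death and the only applicable rule censors it, so median DOR is biased upward whenever a responder dies without documented progression. Under constant hazards the factor is 1/(1-f): 5% to 25% for an assumed f of 5% to 20%, and nothing at f = 0. The direction is certain, but the size cannot be known from the documents.

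The planned log-rank and Cox comparison conditions on response, so its hazard ratio and p-value are not protected by randomisation and should not support a treatment claim. The likely harm is a shifted median and a result that is hard to interpret. Under the assumed response rates and prognostic spread, the false-positive rate stays at about 5% to 8%. The primary analysis is not affected.

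**What to change.** 1. In Protocol section 2 and 10.4.5, and in SAP 5.1 and 5.2, define DOR as the time from first documented CR/iCR or PR/iPR to progression or death from any cause, whichever is first.
2. Reconcile Protocol 7.6.8, which starts the clock at randomisation, with the other definitions. State the start date and the censoring rule once, and repeat them in the SAP.
3. Label the comparison of DOR between arms as descriptive: Kaplan-Meier medians with confidence intervals by arm. Do not use a hazard ratio or p-value among responders as evidence of a treatment effect.
4. Optional: if a comparison that keeps randomisation is wanted, analyse time in response over all randomised patients, with non-responders counted as zero. This is a new estimand that needs its own time horizon and its own rules for death, resection and censoring, so it is not required to settle this point.

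Items 1 to 3 cost a wording change and a small programming change. No new data are needed, because progression and death dates are already collected for PFS and OS. Median DOR becomes slightly shorter, and the responder-only p-value no longer supports a claim.

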### **5.3. Missing data**

Number of missing data will be reported throughout all analyses. It is expected that the number of missing will be low and thus no missing values handling approach is planned. In the case the number of missing will show to be more substantial than expected however, an appropriate approach like for example weighting or multiple imputation will be considered.

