5.5 Duration of therapy

The **control arm** will consist of intermittent treatment with the Nordic FLOX regimen in terms of 8 cycles (16 weeks) before a break until disease progression, when therapy is reintroduced and administered for another 8 cycles before a new break. This go-and-stop schedule, which is chosen because continuous FLOX treatment commonly causes unacceptable toxicity in the palliative setting, will be continued until progressive disease on ongoing therapy (defining PFS in terms of failure of treatment strategy), unacceptable toxicity, withdrawal of consent, or death, whichever occurs first.

The estimated median PFS in the control arm is 9 months (*i.e.*, 39 weeks), as detailed in [Chapter 10](#). During this period, it is assumed that the ‘average’ patient will receive 1 full go-and-stop treatment sequence, consisting of 16 weeks of active therapy followed by 8 weeks of break until disease progression, before the second treatment period results in progressive disease after 16 weeks on ongoing therapy; hence, a PFS of 40 weeks. During the entire treatment, this patient will receive 2 sequences of active therapy, each containing 8 FLOX cycles.

The **experimental arm** will consist of repeat 2 cycles of the Nordic FLOX regimen followed by 2 cycles of nivolumab for a total of 8 individual cycles (16 weeks) before a break until disease progression, when therapy is reintroduced and administered for another total of 8 individual cycles before a new break. This go-and-stop schedule will be continued until progressive disease on ongoing therapy (defining PFS in terms of failure of treatment strategy), unacceptable toxicity, withdrawal of consent, or death, whichever occurs first.

[figure not shown]

Figure 4 – the experimental treatment arm.

The estimated median PFS in the experimental arm is 18 months (*i.e.*, 78 weeks), as detailed in [Chapter 10](#). During this period, it is assumed that the ‘average’ patient will receive 3 full go-and-stop treatment sequences, each consisting of 16 weeks of active therapy followed by 8 weeks of break until disease progression, before the fourth treatment period results in progressive disease after 8 weeks on ongoing therapy; hence, a PFS of 80 weeks. During the entire treatment, this patient will receive 4 sequences of active therapy, each containing 4 cycles each of FLOX and nivolumab.

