Laboratory analyses ¹³	X	X ¹⁴	X ¹⁴	X ¹⁴	X ¹⁴	
Urine analysis ¹⁵	X	X ¹⁴	X ¹⁴	X ¹⁴	X ¹⁴	
Treatment administration						
FLOX						
Nivolumab						
Evaluation procedure(s)						
CT ¹⁷	X	X				
Correlative study procedures						
Whole blood sampling						
Plasma and serum sampling	X	X				
PBMC sampling ¹⁹	X	X				
Functional MR liver acquisition ^{19,20}						
Liver/peritoneal biopsy sampling ²¹						

- 1 Repeat after break period with disease progression, continue until progressive disease on ongoing therapy.
- 2 Until disease progression.
- 3 Analysis on primary or metastatic tumor.
- 4 Only at visit 2.
- 5 By completion of the active therapy of the first treatment sequence (after 16 weeks), *i.e.*, at first visit in first treatment break.
- 6 Until all study drug-related AE are resolved, have returned to baseline, or are deemed irreversible; reported for at least 100 days after last dose administration of IMP.
- 7 To be undertaken if clinically indicated from V1 onward, but mandatory at the 30 days safety follow-up visit.
- 8 May be omitted if full physical examination has been undertaken 14 days or less prior to the first dose of trial treatment.
- 9 For WOCBP.
- 10 Within 24 hours prior to the start of study drug.
- 11 Every 4 weeks.
- 12 Every 4 weeks; in the control arm, for 30 days after the last dose of study drug; in the experimental arm, for 160 days after the last dose of study drug.
- 13 Laboratory tests: Hb, HCT, WBC (including differential counting), platelets, liver factors (ALT, AST, ALP, LDH, GGT, total bilirubin, total albumin, INR), creatinine or urea, Na, K, Ca, Mg, phosphate, glucose, TSH, free T4, CEA, Ca19.9, Ca125.
- 14 Until all study drug-related abnormalities are resolved, have returned to baseline, or are deemed irreversible.
- 15 Dipstick.
- 16 FLOX in control treatment arm, nivolumab in experimental treatment arm.
- 17 In addition to computed tomography (CT) scan, MR scans or other radiologic evaluations will be performed if indicated.
- 18 Baseline CT scan must be taken within 28 days prior to the start of study drug.
- 19 Participation is optional for study centers.
- 20 Patient must not present contraindication to the procedure. Procedure must be done before a metastatic lesion in the liver/peritoneum is sampled.
- 21 Baseline sampling is mandatory; follow-up sampling is optional.

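### The week-16 quality-of-life form goes only to patients who reach the first treatment break, so the week-16 arm means are selected by outcome; anchoring the form to 16 weeks from randomisation is a cheap improvement

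*SAP*

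**What the plan says.** SAP 5.3 promises to report the number of missing data in all analyses. It then says "It is expected that the number of missing will be low and thus no missing values handling approach is planned". If missing data turn out more substantial, "an appropriate approach like for example weighting or multiple imputation will be considered". It gives no trigger, model or target quantity, and SAP 5.4 plans no further analyses.

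SAP 5.1 defines the QoL assessment as "assessment undertaken at study enrolment, completion of the active therapy of the first treatment sequence (after 16 weeks), and disease progression". Footnote 5 of the Protocol flow chart (section 6) ties the middle assessment to finishing the first sequence and places it "at first visit in first treatment break". The only other questionnaire boxes are at V0 and at the end-of-study visit, which is held when treatment is discontinued. Visits V1-V8 and the withdrawal, safety and follow-up columns have none.

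Protocol 5.5 sets the first sequence at "8 cycles (16 weeks) before a break until disease progression, when therapy is reintroduced". It ends treatment at progression on ongoing therapy, unacceptable toxicity, withdrawal of consent or death.

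SAP 5.2 presents mean scores with 95% CIs at each time point. It compares the arms by a linear mixed model with time, arm, their interaction and random patient effects.

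**The concern.** Whether a patient receives the week-16 form depends on still being on treatment at the end of the first sequence. Patients who stop earlier are those who progress, have unacceptable toxicity, withdraw or die, so the absence of the form is linked to outcome. If the study hypothesis is true, fewer experimental than control patients stop early, so the selection also differs by arm.

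The third assessment, at progression, falls at different times in different patients. Week 16 is thus the only post-baseline comparison at a nominal common time. Protocol section 3 and SAP 2.1 name QoL among the aims for which superiority is investigated. EQ-5D-5L is one of the instruments affected, and SAP 5.1 plans quality-adjusted life years for the cost analysis. If the weakest controls are absent from the week-16 mean more often than the weakest experimental patients, a real QoL benefit would be understated. A later statistical remedy cannot fully replace forms that were never handed out.

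**Working it through.** **Inputs**
- Median PFS 9 months (39 weeks) in controls and 18 months (78 weeks) in the experimental arm: Protocol 5.5.
- Exponential PFS, HR 0.5, 80% power, 5% level, log-rank test, 10% censoring, 50 per arm: Protocol 10.1 and SAP 2.3.
- Scans every 8 weeks: Protocol 7.6.5. The flow chart shows one on-treatment CT in a sequence, at V5 (week 8), then CT in the break.
- First break visit taken as week 16, as footnote 5 states.

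**The plan's own figure.** The documents give no number for missing QoL, only that it will be low. The same assumptions reproduce the sample size. Freedman's formula with two-sided 5% gives 7.849 × ((1 + 0.5)/(1 − 0.5))² = 70.6, so 71 events. Then 71/0.9/2 = 39.4, so 40 per arm, as stated. With the adjustments, 80 × 1.05 × 1.20 = 100.8, against the stated 100. The medians used below are therefore those that sized the trial.

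**Share with a PFS event by week t:** 1 − 2^(−t/median). In the first 16 weeks every patient is on active therapy, so any progression is also failure of strategy.

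| | Control | Experimental |
|---|---|---|
| By week 8 | 1 − 2^(−8/39) = 13.3% | 1 − 2^(−8/78) = 6.9% |
| By week 16 | 1 − 2^(−16/39) = 24.7% | 1 − 2^(−16/78) = 13.3% |
| Of 50, by week 8 | 6.6 | 3.4 |
| Of 50, by week 16 | 12.4 | 6.6 |

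**Which row applies.** Progression found at the week-8 scan ends treatment before the break. Progression arising in weeks 8-16 is mostly found at the week-16 scan, when the form is due. The week-8 row is therefore the better estimate. The week-16 row is the upper figure for PFS events, and would apply only if every event in weeks 8-16 were a death or were detected clinically before the scan.

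**Other early stops.** If an extra 5-10% in each arm stopped for toxicity or withdrawal (assumption; the documents give no rate), the week-8 shares become:
- control: 1 − 0.8675 × 0.95 = 17.6% to 1 − 0.8675 × 0.90 = 21.9%
- experimental: 1 − 0.9314 × 0.95 = 11.5% to 1 − 0.9314 × 0.90 = 16.2%

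**Effect on the raw week-16 means.** If patients without the form would have scored d points lower than those with it, equally in both arms, each available-case mean is too high by share × d. The arm difference (experimental minus control) is then off by (experimental share − control share) × d. Assume d = 10-20 on a 0-100 scale where higher is better:
- week-8 shares: −6.4 percentage points × 10-20 = −0.6 to −1.3 points
- week-16 shares: −11.5 percentage points × 10-20 = −1.2 to −2.3 points

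**The case against.** A reader might infer that up to a quarter of controls have no post-baseline QoL at all. The documents do not support that. Patients who stop alive have a form at the end-of-study visit, and Protocol 7.7.4 requires the applicable final-visit activities whenever someone discontinues or withdraws early. What they lack is a week-16 form. The 25% is also an upper figure, given the scan schedule.

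The experimental share may be below 7%, because progression there needs confirmation 4-8 weeks later (Protocol 7.6.4 and 7.6.6) and treatment may continue meanwhile (Protocol 5.7.2.4). That is a fair correction to the share, but it widens the gap between arms rather than closing it.

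A reader might also take the absence of a handling plan to mean a complete-case analysis, and so read the 0.6-2.3 points as the bias of the planned test. That does not follow. The mixed model uses every available form, including baseline and discontinuation forms, and is valid if data are missing at random. The point figures concern only the raw week-16 means. Still, the SAP neither states that assumption nor tests it.

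The size is modest and rests on an assumed deficit. With an assumed SD of 20 and the 95 patients left after removing 5% non-MSS cases, the week-16 shares leave 47.5 × 0.7525 ≈ 36 control and 47.5 × 0.8675 ≈ 41 experimental forms. The standard error is 20 × √(1/36 + 1/41) ≈ 4.6 points, so even 2.3 points is about half a standard error. This stands.

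Finally, the assessment is defined by completing the first sequence, so a form that was never due is arguably not missing in the sense of SAP 5.3, and a score after death is undefined rather than missing. SAP 5.3 also promises missing counts and names fallback methods. These are good reasons not to call SAP 5.3 wrong as written. They do not change whom the week-16 means describe.

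**Conclusion.** The point holds as a cheap improvement, not as an error that invalidates the QoL analysis. On the plan's own exponential medians, about 13% of control and 7% of experimental patients would miss the week-16 form through progression or death by the week-8 scan. The upper figures for PFS events are 25% and 13%; toxicity stops and withdrawals come on top. An expectation of few missing data fits poorly with these rates.

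The week-16 arm means describe patients who reached the break, a selection that depends on outcome and, under the study hypothesis, differs about twofold between arms. The resulting shift in the raw difference is about 0.6-1.3 points against the experimental arm, up to 2.3 with the week-16 shares. It rests on the assumed 10-20 point deficit, equal in both arms. The selection and its imbalance do not depend on that assumption; they rest on the flow chart and the plan's PFS assumptions.

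**What to change.** **Protocol flow chart (footnote 5), Protocol 7.10.1 and SAP 5.1:** give the QoL form 16 weeks after randomisation to every living, consenting patient, whether or not still on treatment, on paper or by phone.

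**SAP 5.3:**
- replace the statement that missing data will be low with the expected rates above;
- report completion by arm and reason, beyond the counts already promised;
- state that the mixed model assumes data missing at random;
- say how deaths before week 16 are handled;
- add one delta-adjusted sensitivity analysis for the week-16 contrast.

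**Cost:** the expected number of early PFS events is 6.6 + 3.4 = 10 on the week-8 shares and 12.4 + 6.6 = 19 on the week-16 shares. Some of these patients will have died and some will complete a form at week 16 anyway, while toxicity stops add a few, so roughly 5-20 extra questionnaires and one added analysis. No treatment rule changes.
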